4.1 Recruitment and retention

The date of first and last participants randomised, the number of participants randomised (overall and by site) will be reported.

Using the screening population, a tabulation/graphic will be produced that contains information with which to construct a STARD-style flow chart], to show the flow of participants through the different phases of the trial, as follows:

1. Number of participants assessed for eligibility
2. Number excluded, including
 - a. Number not meeting inclusion criteria
 - b. Declined to participate
 - c. Other reasons
3. Number of eligible participants who consented – reasons for non-inclusion prior to randomisation will be categorised.
4. Number of participants recruited
5. Number of participants who withdrew consent – reasons will be categorised.
6. Number of participants to complete 1 year follow-up

The number and percentage of deaths and withdrawals will be reported.

A summary of number of participants recruited per month per site shall also be presented.

4.2 Baseline data

No formal statistical testing will be performed. Using the ITT population, the following baseline assessment results shall be summarised overall:

- age in years,
- gender (male, female, other),
- ethnicity,
- physical or mental health condition (Y/N),
- working status (fulltime, part time, unemployed, retired or student),
- weight (kg),
- height (cm),
- BMI (kg/m²),
- smoking status (Y/N former),
- alcohol consumption (none/negligible, average units per week),
- physical activity level (low, moderate or vigorous),
- type of diabetes (I or II),
- concomitant diseases (malignancy, hypertension, stroke, heart attack, high cholesterol, angina, retinopathy, chronic kidney disease),

- foot history (previous diabetic foot ulcer and/ or minor/ major amputation),
- PAD symptoms,
- medications list (currently taking antiplatelets, anticoagulants, inflammatories, lipid modification, antihypertensives, other),
- foot examination (infection, ulceration),
- pedal pulse examination (for right and left leg – dorsal pedis, posterior tibial, neuropathy),
- wifi classification (I, II or III),
- index test results (Audible handheld Doppler, Visual handheld Doppler, PAD-scan (only in 4 centres), Ankle-brachial pressure index (ABPI), Toe-brachial pressure index (TBPI) & Exercise ABPI i.e. ABPI performed following repetitive heel raising).

4.3 Graphical analysis

We will produce boxplots, i.e. a graphical summary of the distribution including mean, median, first and third quartile, minimum and maximum values, to compare each test score according to the reference standard. Descriptive statistics will also be provided. This will be summarised overall and by site where feasible.

4.4 Primary outcome

The primary outcome will be the sensitivity of each diagnostic test compared against the reference test at diagnosing PAD. Sensitivity refers to the ability in correctly identifying participants who have PAD.

Tests generating continuous outcomes (ABPI, TBPI and exercise ABPI) shall also be evaluated for performance based on optimised thresholds derived from Receiver Operating Characteristics (ROC) analysis. This will involve calculating, for a range of cut-points, the sensitivity of each continuous outcome diagnostic test with respect to the reference test for assessing PAD. This will determine how accurate each test is in identifying patients who will develop PAD. It is desirable to have both high sensitivity and high specificity (see Secondary outcomes).

Table 1

		CMT/MRA Reference Test		
		PAD	Non PAD	Total
Diagnostic test	Positive	A (True Positives; TP)	B (False Positives; FP)	$T_{Test Positive}$
	Negative	C (False Negatives; FN)	D (True Negatives; TN)	$T_{Test Negative}$
		$T_{Disease}$	$T_{Non Disease}$	Total

4.5 Secondary analyses

4.5.1 ROC analysis

The following analyses will be obtained through the same ROC analysis performed in the primary outcome analysis for each diagnostic test:

- a) The specificity of each diagnostic test compared against the reference test. Specificity refers to the ability in correctly identifying participants who do not have PAD. Tests generating continuous outcomes (ABPI, TBPI and exercise ABPI) shall also be evaluated for performance based on optimised thresholds derived from Receiver Operating Characteristics (ROC) analysis. This will involve calculating, for a range of cut-points, the specificity of each continuous outcome diagnostic test with respect to the reference test for assessing PAD.

- b) The positive likelihood ratio (i.e. the ratio between the probability of a positive test result given the presence of PAD and the probability of a positive result given the absence of PAD; sensitivity/(1-specificity)) and the negative likelihood ratio (i.e. the ratio between the probability of a negative test result given the presence of PAD and the probability of a negative result given the absence of PAD, (1-sensitivity)/specificity) shall be calculated.
- c) The positive predicted value (i.e. the probability of the presence of PAD when the test is positive; a/(a+b)) and the negative predicted value (i.e. the probability of the absence of PAD when the test is negative; d/(c+d)) shall be presented.
- d) The diagnostic odds ratio is along with the associated 95% CI (calculated at 99% to adjust for the five or six comparisons) will be presented.
- e) Inter and intra-rater reliability shall also be assessed for each diagnostic test and for the reporting of the reference tests (as described in the Section 2)

4.5.2 *Combinations of tests*

The protocol says that an approach described by Pepe and Thompson [2] was to be used which examines linear combinations of the underlying tests was to be used. However, the paper specifies that this method is extremely complex when we wish to consider including more than two tests in the model. So that final models are comparable, a logistic regression approach shall be used instead.

Different combinations of tests will be explored to see if using more than one index test proves to have incremental diagnostic value. A logistic regression analysis shall be performed on each combination below and presented in a table including the number and percentage of observations in each test against PAD diagnosis, odds ratios, 95% confidence intervals, and the overall C statistic for that model.

There are three different technologies when looking at the Index Tests:

- Doppler – Audible; Visual
- Brachial Pressure Index (BPI) – Toe (TBPI); Ankle (ABPI)
- Exercise

The following combinations shall be explored:

1. Audible Doppler; TBPI
2. Audible Doppler; ABPI
3. Audible Doppler; Exercise
4. Visual Doppler; TBPI
5. Visual Doppler; ABPI
6. Visual Doppler; Exercise
7. TBPI; ABPI
8. TBPI; Exercise
9. Audible Doppler; TBPI; ABPI
10. Audible Doppler; TBPI; Exercise
11. Visual Doppler; TBPI; ABPI
12. Visual Doppler; TBPI; Exercise

The results of these analyses might benefit from being presented in a forest plot to clearly show the differences between the different combinations. This may be performed after initial analysis.

Note that this analysis is exploratory and as such there is no need to consider multiple comparisons.

4.6 Sensitivity analysis

Missing data

A sensitivity analysis may be performed in which missing primary outcome data are imputed. The robustness of the findings to any observed patterns of missing data will be assessed, which are expected to differ by test. The imputation method will be determined at time of analysis, taking into consideration the choice of assumptions such as missing at random (MAR) or missing not at random (MNAR) depending on reasons for loss to follow-up[3].

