Exercise ABPI traditionally requires a treadmill. This limits its use in primary care, where a treadmill is not available. Additionally, the results of the patient and public involvement (PPI) work suggest that 43% of patients will not be able to walk on a treadmill (due to disability, frailty or DFU) and that an additional visit to a vascular laboratory for this test would not be acceptable. To ensure patient acceptability, repetitive heel raising will be used. This can be performed in clinics, has excellent correlation with treadmill testing (28,29) and has been advocated by the American Heart Association (30). Our PPI focus group considered this test acceptable.

The exercise ABPI protocol, will consist of 50 consecutive repetitions of active dorsiflexion whilst standing (28). The knees should be kept fully extended. Participant will be allowed fingertip support against a wall to assist with balance. The protocol will be symptoms limited, so that premature termination of exercise will be permitted if the subject experiences lower limb discomfort, chest pain, shortness of breath or feels unwell for any other unspecified reason. Instances of premature termination, and accompanying reasons, will be recorded. ABPI will be measured using the same methodology as outlined above.

In some patients, exercise ABPI may not be possible due to deformities of the foot, e.g., those with forefoot amputation, Charcot foot syndrome and forefoot plantar ulceration. Foregoing exercise ABPI will be left to the clinical teams discretion. Reasons for foregoing exercise ABPI will be documented.

- **TBPI**

Measurements will be made using the Huntleigh toe pressure kit (Huntleigh Healthcare Ltd., Cardiff) employing an infrared sensor placed on the hallux.

Brachial artery pressures from both arms will be taken and the highest reading used to calculate the TBPI.

- **Audible handheld Doppler**

Audible CW Doppler interrogation of the dorsalis pedis and posterior tibial artery (Dopplex D900 Audio only Doppler, Huntleigh Healthcare Ltd., Cardiff).

- **Visual handheld Doppler**

Visual CW interrogation of the dorsalis pedis and posterior tibial artery using the handheld Huntleigh Digital Dopplex device (Huntleigh Healthcare Ltd., Cardiff). The pseudonymised visual blood flow waveforms will be saved and may be used for future analysis.

- **PAD-scan (in selected centres)**

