8. STATISTICAL ANALYSES

8.1 Sample Size and power considerations

Summary of sample size calculations

Assuming PAD prevalence of 50%, with 255 with PAD and 255 without PAD, the study will have 90% power to estimate an assumed sensitivity (or specificity) to a precision of the half width of the 95% confidence interval of 8.2%. For a sensitivity (or specificity) of 80% this half width would increase to 10.2%. The level of significance was set at 1% to adjust for the 5 tests and ensure the overall level of significance does not exceed 5%. Power calculations used R.4.0.0 power.diagnostic.test in package MKmisc. The sample sizes for estimating likelihood ratios will also be estimated.

In the TrEAD study, PAD prevalence was 66%. As there will also be recruitment from primary care, with a lower PAD prevalence (34), the estimate to reflect the findings of our systematic review have been adjusted; prevalence of 50% across 18 studies (11). In TrEAD, TBPI could not be performed in 20% of patients. A similar proportion may be unable to tolerate exercise ABPI. It is estimated that 10% of patients may drop out prior to the reference test. Therefore, the sample size has been inflated by the cumulative missingness across all groups (30%) to be certain of having enough power for each and every test comparison. Thus, we aim to recruit a total of 730 patients.

During a study monitoring meeting in February 2023 with the funder, NIHR, it was agreed for the study sample size to be reduced from 730 to 584 based on the current attrition rate of 13% (as opposed to 30% estimated when the trial was designed). To account for those participants that may not get their reference test performed within the set time frame, a final recruitment target of 600 was agreed with the NIHR in August 2023.

Details of sample size calculations

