8.4 Statistical Analysis

The five individual tests (and the sixth exploratory test in four sites) will be compared against the reference test (CTA/MRA), calculating standard diagnostic accuracy metrics of sensitivity, specificity, predictive values, likelihood ratio, and diagnostic odds ratio (using the bivariate model approach implemented in R). 95% confidence intervals calculated at 99% to adjust for the five comparisons will be presented. The robustness of the findings to any observed patterns of missing data will be assessed, which are expected to differ by test. A multiple imputation approach will be used assuming the data are missing at random. In addition, and probably more consistent with the likely missing data generating mechanisms, sensitivity type analyses assuming the data are missing not at random (i.e. informatively missing) will be explored. This would attempt to identify different types of missing data by an underlying reason or reasons, and then imputing values that capture plausible measurements for those missing data. The ?-adjustment approach given by van Buuren will be followed ([Flexible Imputation of Missing Data, Chapman and Hall, 2018, section 3.8ff](#)), and also the recommendations of Molenberghs & Kenward ([Missing Data in Clinical Studies, Wiley, 2007; Section 19ff on sensitivity analyses](#)). These approaches would allow the set of reasons for missing values to vary across the tests. The purpose is to stress the calculated findings to test their robustness to the observed patterns of missing data.

The subgroups of disease severity (both clinically and radiologically defined as detailed below) will be explored and those with/without neuropathy or DFU. The subgroups in the Statistical Analysis Plan will be pre-specified. Any further subgroup analysis (e.g. if suggested later by new data external to the study) will be labelled exploratory. Pre-specified subgroup analyses will be unlikely to be adequately powered. Clinical severity will be graded according to the severity of symptoms (from least to most severe; asymptomatic, intermittent claudication, rest pain and tissue loss). Severity will be measured radiologically using the ANGIO-score as outlined in section 5.7. Both will be analysed as pre-specified subgroup analyses in the Statistical Analysis Plan.

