3.3 General

In general terms, categorical data will be presented using counts and percentages, whilst continuous variables will be presented using the mean, median, standard deviation (SD), minimum, maximum, Q1, Q3, inter-quartile range (IQR) and number of patients with an observation (n).

The comparison group here is diagnostic technique, so where applicable results will be split by diagnostic tests.

A further reporting metric is the number of participants who were included in the analysis, which will be supported for each of the primary (section 4.4) and secondary (section 4.5) analyses by the preparation of a STARD-style flow chart showing the 'pipeline leakage' from participants who were enrolled, to participants included in the analysis.

Where there is missing data for an outcome variable, in the first instance, those individual cases will be removed from any statistical analysis relating to that outcome variable (i.e. complete case analysis), unless otherwise specified. In tabulations, numbers of missing observations will be provided, but percentages will not include them.

All analysis and data manipulation will be carried out using SAS [1] unless otherwise stated.

Qualitative or health economic analysis will not be covered by this SAP. However, data from the statistics report may be used for health economics analyses.

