3.4 Determining PAD diagnosis from Index test results

For each index test, a participant is defined as having a positive result in PAD if they have recorded the following criteria ***in either vessel (i.e. Dorsalis pedis OR Posterior tibial):***

1. Audible waveform assessment: monophasic waveform.
- 2a. Visual waveform assessment: monophasic ***OR*** biphasic waveforms with adverse features.
- 2b. Podiatry ankle duplex (PAD) scan: monophasic or biphasic waveforms with adverse features.
3. ABPI: ABPI (DP) ≤ 0.9 ***OR*** ABPI (PT) ≤ 0.9 in the limb being assessed.
4. TBPI: TBPI < 0.75 in the limb being assessed.
5. Exercise ABPI: Exercise ABPI (DP) ≤ 0.9 ***OR*** Exercise ABPI (PT) ≤ 0.9 in the limb being assessed.

For tests that have measurements for the right and left limbs, we are only interested in the limb that was assessed, i.e. in response to the question in section ‘Index Tests (Repeat 1) ‘Which limb is being assessed?’.

Each criteria assessment above, except TBPI, has two vessels, a ‘Dorsal pedis artery (DP)’ and ‘Posterior tibial artery (PT)’. If both vessels are completed then a PAD diagnosis is determined as follows:

- DP(+ve) + PT(+ve) = PAD(+ve)
- DP(+ve) + PT(-ve) = PAD(+ve)
- DP(-ve) + PT(+ve) = PAD(+ve)
- DP(-ve) + PT(-ve) = PAD(-ve)

There may be a case where either the DP or PT vessel has been recorded, not both. When this is the case a comment as to why this vessel is missing should be recorded:

- DP(+ve) + PT(missing) = PAD(+ve)
- DP(missing) + PT(+ve) = PAD(+ve)
- DP(-ve) + PT(missing) = PAD(inconclusive)
- DP(missing) + PT(-ve) = PAD(inconclusive)

When a diagnosis of PAD is inconclusive, these cases will be recorded and reported but shall not be used in the final analysis.

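### SAP 4.6 makes the protocol's missing-data imputation optional, leaves its method open, and bases it on loss to follow-up instead of on why an index test was not done

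*SAP*

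**What the plan says.** **Protocol 8.4** presents imputation as a test of robustness to missing-data patterns that are expected to differ by test. The MAR part is firm: "A multiple imputation approach will be used assuming the data are missing at random". The MNAR part is softer: "sensitivity type analyses assuming the data are missing not at random (i.e. informatively missing) will be explored". The protocol nevertheless calls MNAR probably the more realistic mechanism, names an adjustment method from a cited textbook, and lets the set of reasons vary across tests.

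**SAP section 2** reproduces that text under a heading that labels it as the protocol's statistical methods. **SAP 3.1** says that every protocol analysis except the internal pilot is addressed.

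**SAP 3.3** sets the default for missing outcome data: "in the first instance, those individual cases will be removed from any statistical analysis relating to that outcome variable (i.e. complete case analysis". The sentence goes on to allow exceptions specified elsewhere. **SAP 3.4** adds that when only one vessel is recorded and it is negative, the result is inconclusive: "these cases will be recorded and reported but shall not be used in the final analysis". **SAP 4.4**, on the primary outcome, has no missing-data rule of its own.

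**SAP 4.6** is the SAP's own plan for missing data: "A sensitivity analysis may be performed in which missing primary outcome data are imputed". It says that robustness will be assessed. It defers the imputation method to the time of analysis and makes the choice between MAR and MNAR depend on reasons for loss to follow-up.

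On expected missingness, protocol 8.1 states: "In TrEAD, TBPI could not be performed in 20% of patients". It allows a similar proportion for exercise ABPI and 10% dropout before the reference test. Protocol 5.7 states: "In some patients, exercise ABPI may not be possible due to deformities of the foot". Its examples are forefoot amputation, Charcot foot and forefoot plantar ulceration.

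**The concern.** Sensitivity is the only primary endpoint, and SAP section 1 describes the study as powered to compare five index tests. With complete-case analysis, each test is scored on the participants in whom it gave a usable result. If those groups differ in ways related to test performance, part of any difference between tests reflects who could be measured.

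The protocol anticipated this and planned a check. Under SAP 4.6 an analyst could omit imputation altogether, or choose its assumptions after seeing the results, and still comply with the section.

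The stated basis for the choice is also a poor match. Index tests are done at visit 1 and the reference scan within six weeks. Loss to follow-up can describe a missed scan. It does not describe a toe pressure that could not be measured or a heel-raise test that the clinical team decided to forgo, and these are the larger expected gaps.

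**Working it through.** **1. Texts side by side**

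| Item | Protocol 8.4 (copied in SAP 2) | SAP 4.6 |
|---|---|---|
| MAR multiple imputation | will be used | may be performed |
| MNAR analyses | will be explored | one option, chosen later |
| Method | named adjustment approach | decided at time of analysis |
| Basis | reasons that vary by test | reasons for loss to follow-up |

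The SAP says that it was written from protocol version 5.0, and the current protocol is 7.0. This does not explain the difference, because the SAP's own copy of the protocol text contains the firm sentence.

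**2. The plan's missingness figures**

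Inputs from protocol 8.1: 510 evaluable participants, 50% PAD prevalence, and cumulative missingness of 20% + 10% = 30%, later replaced by observed attrition of 13%.

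- 510 / (1 − 0.30) = 728.6, rounded up to 729 (stated 730).
- 510 / (1 − 0.13) = 586.2, rounded up to 587 (stated 584, later raised to 600).

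Both reproduce closely, so test-specific missingness is part of the plan's own arithmetic.

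**3. How far missing results could move a sensitivity (illustration only)**

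Let *s* be the sensitivity in measured PAD limbs, *m* the share of PAD limbs without a result, and *q* the unknown sensitivity in those limbs:

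whole-cohort sensitivity = (1 − *m*) × *s* + *m* × *q*.

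Take *s* = 0.60 (TBPI in the earlier TrEAD study, protocol section 1) and *m* = 0.20 (protocol 8.1). It is assumed that missingness is the same with and without PAD.

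- Lower bound, *q* = 0: 0.80 × 0.60 = 0.48.
- Upper bound, *q* = 1: 0.48 + 0.20 = 0.68.

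For other values of *m*:

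- *m* = 0.13: 0.87 × 0.60 = 0.522, up to 0.522 + 0.13 = 0.652.
- *m* = 0.30: 0.70 × 0.60 = 0.42, up to 0.42 + 0.30 = 0.72.

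**4. Comparison with sampling error**

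The planned intervals are at the 99% level, so half-width = 2.576 × √(0.60 × 0.40 / *n*).

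- 600 recruited, 20% missing: *n* = 600 × 0.5 × 0.80 = 240, half-width 8.2 points.
- 584 recruited, 30% missing: *n* = 584 × 0.5 × 0.70 = 204, half-width 8.8 points.

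At *m* = 0.20 the bounds lie 12 points below and 8 points above the observed 60%. The lower shift exceeds the 99% half-width, and the upper one is about equal to it. A complete-case interval contains none of this uncertainty.

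**The case against.** The strongest reply is that nothing has been withdrawn. The firm wording stands in SAP section 2, SAP 3.1 says that the protocol's analyses are covered, and SAP 4.6 itself says that robustness will be assessed. Where the SAP does drop a protocol method (combinations of tests, SAP 4.5.2), it says so and gives a reason, and it says nothing of the kind here. So a reader who infers that the SAP abandons the robustness check goes too far. What remains is an inconsistency. Section 2 is a labelled copy of the protocol, section 4.6 is the operative text, and a promise to assess robustness by a method still to be chosen constrains very little.

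Three other stronger readings are tempting, and the documents do not support them.

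- *Complete case as the primary analysis breaks the protocol.* It does not. Protocol 8.4 never makes imputation primary.
- *TBPI and exercise ABPI are scored only on easier feet, while the Doppler tests are scored on nearly everyone.* Protocol 5.7 gives foot deformity, not PAD severity, as the reason for forgoing exercise ABPI. No reason is given for the 20% TBPI failure, and no failure rate is given for Doppler. The inconclusive-vessel exclusion in SAP 3.4 applies to the Doppler tests and not to TBPI.
- *The likely bias is as large as the sampling error.* If unmeasured limbs had sensitivity between 30% and 90% (assumed), the whole-cohort value would run from 54% to 66%. That shift of at most 6 points is below the half-width at *n* = 204 of 6.7 points (95%) or 8.8 points (99%). Only the extreme bounds reach it.

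It is also fair to say that the documents do not explain what the 13% attrition covers. If all of it were TBPI failure, the bounds narrow to 52.2% and 65.2%. Finally, scoring a failed test as negative (numerically the 48% bound) answers a different question, and technical success is a separate secondary endpoint.

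**Conclusion.** The conflict is real and concerns the primary endpoint. SAP 4.6 turns a committed MAR imputation into an option, fixes no method for the MNAR work, and bases the choice on a mechanism that does not describe the main expected gap. It disagrees both with protocol 8.4 and with SAP section 2.

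The documents support the possibility of selection: about 20% missing for each of two tests, with foot-related reasons stated for exercise ABPI. They do not establish its direction or size. The bounds of 48% and 68% rest on 60% observed sensitivity, 20% of PAD limbs missing and equal missingness by disease status. They show what complete-case intervals leave out and do not predict bias.

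This should be fixed before database lock. It does not invalidate the primary analysis, and complete case can remain primary.

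**What to change.** Amend SAP 4.6 before database lock, so that it agrees with SAP section 2 and protocol 8.4:

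1. Change *may* to *will* for the imputation analysis.
2. Specify MAR multiple imputation for each index test, using the reference result, ANGIO score, DFU, neuropathy, previous amputation and the other index tests.
3. Specify an MNAR delta-adjustment by test and by recorded reason for non-performance, with the range of adjustments stated in advance.
4. Replace loss to follow-up, as the basis for the assumptions, with the reasons why the index test or reference scan was not obtained.
5. As a supportive analysis, repeat the between-test comparisons in participants who have all five index tests. This goes beyond what the protocol promises, but it removes the difference in who was measured.

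The cost is SAP wording and modest extra programming. No new data are needed, because protocol 5.6 and 5.7 already require inability, refusal and discontinuation of index tests, and the reasons for forgoing exercise ABPI, to be documented.
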